9.2.4.2 Secondary Efficacy Endpoint Analyses

Secondary efficacy analyses will be based on the Efficacy Evaluable Population. The comparison of active versus placebo treatment will be tested at the two-sided 0.05 significance level.

The following are the set of continuous secondary efficacy endpoints:

- Change from baseline in the weekly SBM rate during the Fixed Dose period
- Change from baseline in stool ease of passage during the Fixed Dose period
- Change from baseline in stool consistency during the Fixed Dose period
- Change from baseline in suppository/enema use during the Fixed Dose period

All continuous secondary efficacy endpoints will be analyzed in the same manner as the primary efficacy endpoint.

The following are the set of dichotomous secondary efficacy endpoints:

- Pro-kinetic bowel response during the Fixed Dose period
- SBM bowel response to ENT-01 during the Fixed Dose period

For the dichotomous secondary efficacy endpoints, the comparison of the ENT-01 versus placebo treatment groups will be performed by means of Fisher's exact test.

The following are the set of time to event secondary efficacy endpoints:

- Time to first CSBM in the Fixed Dose period
- Time to first SBM in the Fixed Dose period
- Time to first rescue medication use in the Fixed Dose period
- Time to event secondary efficacy endpoints will be summarized using Kaplan-Meier methods, comparisons between treatment groups will be made via log-rank tests.
- For the frequency of dose adjustments in the Dose Adjustment period secondary endpoint, the frequency of the number of dose adjustments a subject has from the initial starting dose to the subject's fixed dose will be summarized by treatment group and baseline CSBM strata.
- For the PAC-SYM and PAC-QOL subjective assessments secondary efficacy endpoints, the overall scores from the Fixed Dose period will be analyzed via an ANCOVA model with treatment as a factor and the subject's corresponding baseline score as a covariate. Additional summaries of the individual items will be performed.

9.2.4.3 Exploratory Efficacy Endpoint Analyses:

The analysis methods for the exploratory efficacy endpoints will be provided in the SAP.

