2.2. Randomization Methodology

Randomization occurs after all screening assessments have been completed and after the Investigator has verified that they are eligible. In the first part of the study, patients will be

randomized 3:1 to receive either ENT-01 or placebo; in the second part of the study patients are randomized 1:1 to receive either ENT-01 or placebo. Any patient identification numbers that are assigned will not be reused, even if the patient does not receive treatment. The patient's identification (ID) number will be used on that patient's eCRFs and serious adverse event (SAE) forms.

Randomization will be conducted centrally via an Interactive voice/web-response system (IXRS). The randomization will be stratified by the baseline weekly CSBM rate. Subjects with a baseline CSBM rate of 0-0.9 will begin treatment with 150 mg of ENT-01 or 6 tablets of placebo and Subjects with a baseline CSBM rate of 1.0-2.9 will begin with 75 mg of ENT-01 or 3 tablets of placebo. Note that in the second part of the study, the baseline CSBM criteria of 1.0 – 2.9 was modified to 1.0 – 3.0 (i.e., including subjects with a baseline CSBM rate of 3.0).

Instructions for patient screening, registration, number assignment, and enrollment are referenced in the Interactive Response Technology (IRT) vendor manual.

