4.2. General Statistical Methods and Data Handling

General Methods

All outputs will be incorporated into Microsoft Excel or Word files, sorted and labeled according to the International Conference on Harmonisation (ICH) recommendations, and formatted to the appropriate page size(s).

Tabulations will be produced for appropriate demographic, baseline, efficacy, pharmacokinetic and safety parameters. For categorical variables, summary tabulations of the frequency and percentage within each category (with a category for missing data) of the parameter will be presented. For continuous variables, the mean, median, SD, minimum and maximum values will be presented. Time to event data will be summarized using Kaplan-Meier Methodology using 25th, 50th (median), and 75th percentiles with associated 2-sided 95% confidence intervals, as well as percent of observed event rate and summary statistics for the follow-up time.

Formal statistical hypothesis testing will be performed on the efficacy endpoints with all tests conducted at the 2-sided 0.05 level of significance. Summary statistics will be presented, as well as confidence intervals on selected parameters, as described in the sections below.

For all analyses, baseline will be defined as the most recent measurement prior to the date and time of the administration of ENT-01 or placebo. Therefore, baseline may be on the same day as the dose of study treatment, but prior to the administration of the study treatment.

Computing Environment

All descriptive statistical analyses will be performed using SAS statistical software (Version 9.4), unless otherwise noted. Medical History and Adverse Events will be coding using the latest MedDRA version available upon the study start. Concomitant medications will be coded using the latest World Health Organization (WHO) Drug version available upon the study start.

Methods of Pooling Data

Not applicable to the present study.

Adjustments for Covariates

Statistical analyses for the efficacy endpoints will be adjusted by the randomization strata, the baseline CSBM rate (0 – 0.9 vs. 1.0 – 3.0).

Multiple Comparisons/Multiplicity

Adjustments for multiplicity will not be made for this study.

Subpopulations

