4.6.4 Analysis of Secondary Efficacy Endpoints

All secondary efficacy endpoints will be analyzed based on both the Efficacy Evaluable population and Fixed Dose population.

Continuous Secondary Efficacy Endpoints

The following are the set of continuous secondary efficacy endpoints:

- Change from baseline in the weekly SBM rate during the Fixed Dose period
- Change from baseline in stool ease of passage during the Fixed Dose period
- Change from baseline in stool consistency during the Fixed Dose period
- Change from baseline in suppository/enema use during the Fixed Dose period
- Change from baseline in the overall scores and individual items of PAC-SYM and PAC-QOL subjective assessments during the Fixed Dose period

All continuous secondary efficacy endpoints will be analyzed in the same manner as the primary efficacy endpoint with treatment, baseline CSBM strata, and corresponding baselines as the independent variables in the ANCOVA model and also by summarizing change from baseline

by the specific fixed doses. The same linear trend tests will also be performed on these endpoints.

Categorical Secondary Efficacy Endpoints

The following are the set of categorical secondary efficacy endpoints:

- Dichotomous prokinetic bowel response during the Fixed Dose period
- Dichotomous SBM bowel response during the Fixed Dose period
- Frequency of dose adjustments in the Dose Adjustment period from the initial starting dose to the subject's fixed dose

The dichotomous endpoints will be summarized using count data, frequencies, and odds ratios for comparisons between groups, and analyzed using Fisher's exact test. If there are sufficient numbers in each strata, the analysis may also be performed using the Cochran-Mantel-Haenszel (CMH) test adjusting for the baseline CSBM strata, to compare ENT-01 versus placebo. The frequency of dose adjustment will be summarized by treatment groups and baseline CSBM strata and no formal test will be performed to compare the treatment groups.

Summary statistics will also be presented by specific fixed dose groups for descriptive purposes only.

Time to Event Secondary Efficacy Endpoints

The following are the set of time to event secondary efficacy endpoints:

- Time to first CSBM in the Fixed Dose period
- Time to first SBM in the Fixed Dose period
- Time to first rescue medication use in the Fixed Dose period

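### Responder endpoints are tested by unstratified Fisher's exact test with stratified CMH only optional, against the rule in SAP 4.2; if the two parts are pooled, cohort must be a stratum too

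*SAP*

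**What the plan says.** SAP 2.2 states: "The randomization will be stratified by the baseline weekly CSBM rate". SAP 4.2 (Adjustments for Covariates) draws the consequence without exception: "Statistical analyses for the efficacy endpoints will be adjusted by the randomization strata".

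For the two dichotomous secondary endpoints, SAP 4.6.4 departs from this. They are summarized with "odds ratios for comparisons between groups, and analyzed using Fisher's exact test". Stratification appears only as an option, on condition that each stratum holds enough subjects: "the analysis may also be performed using the Cochran-Mantel-Haenszel (CMH) test adjusting for the baseline CSBM strata". Protocol 9.2.4.2 does not mention CMH; there "the comparison of the ENT-01 versus placebo treatment groups will be performed by means of Fisher's exact test".

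The other formally tested secondary endpoints in the SAP follow the rule: the ANCOVA for continuous endpoints includes the CSBM strata, and the log-rank tests are stratified. The exploratory SAPS-PD responder test (SAP 4.6.5) also uses Fisher, with CMH if numbers allow. SAP 4.2 makes no multiplicity adjustment. Under Subpopulations it also presents results by cohort: part 1 (randomized 3:1) and part 2 (randomized 1:1).

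**The concern.** The responder tests are the unadjusted exception to the SAP's own rule. The wording also leaves two tests of the same endpoint available. The plan does not say how many subjects per stratum are enough for CMH, or which p-value counts if the two disagree.

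Two things are at stake. One is power: Fisher's test on the collapsed table is conservative at these sample sizes, and more so if response differs between strata. The other is validity if the cohorts are combined. Allocation was 3:1 in part 1 and 1:1 in part 2, so cohort is associated with treatment in the pooled table. SAP 4.6.1 shows that the diary questions behind a CSBM differ by cohort, so different response rates are plausible. Neither Fisher nor CMH on CSBM stratum alone allows for that.

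**Working it through.** **Inputs from the documents.** Two-sided 0.05 (SAP 4.2). Part 1: 64 evaluable at 3:1, so 48:16 (SAP 4.1). Part 2: 80 at 1:1 less 10% drop-out (Protocol 9.2.5), so 36:36; or 60 evaluable (SAP 4.1), so 30:30. Pooled: (48 + 36):(16 + 36) = 84:52, or (48 + 30):(16 + 30) = 78:46.

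**Assumed.** Equal strata, placebo response rates, and a common odds ratio of 3. The only response rate in the documents is the uncontrolled 82.4% from phase 2a (Protocol 2.2); no placebo or per-stratum rate is given.

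**The plan's own figure.** No power is stated for the responder endpoints. The part 1 power for the primary endpoint reproduces: noncentrality 1.9 / (2.0 × √(1/48 + 1/16)) = 3.29 on 62 df gives 90.0%, against 90% stated. This confirms only the 48:16 reading.

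**Step 1. Fisher alone.** I enumerated all 2×2 tables, with null rates of 10-90% equal in both strata. True size at nominal 5% is 0.9-2.7% at 30:30, 1.4-2.8% at 36:36, 3.3-4.1% at 78:46 and 3.6-4.4% at 94:58 (all randomized subjects). It can fall lower: 0.15% at 30:30 with a 5% rate.

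**Step 2. Fisher against CMH.** For stratum k with n1 active, n0 placebo, N in total, m responders and x active responders:

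CMH = [Σ(x − n1·m/N)]² / Σ[n1·n0·m·(N − m) / (N²(N − 1))], rejecting above 3.84, without continuity correction.

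The active rate in each stratum has three times the placebo odds (30% becomes 56.25%, 50% becomes 75%). Results are from 400,000 simulations per row, with response rates equal across cohorts:

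| n | Placebo rates by stratum | Fisher size | Fisher power | Unstratified chi-square power | CMH power |
|---|---|---|---|---|---|
| 36:36 | 30% / 30% | 2.7% | 51% | 61% | 61% |
| 36:36 | 30% / 50% | 2.2% | 48% | 58% | 60% |
| 36:36 | 25% / 60% | 1.6% | 40% | 50% | 57% |
| 36:36 | 20% / 75% | 0.7% | 23% | 33% | 48% |
| 84:52 | 30% / 50% | 3.8% | 81% | 84% | 85% |
| 84:52 | 25% / 60% | 2.8% | 75% | 78% | 82% |

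CMH size is 4.8-5.1% in these rows. At 36:36 and 30%/50% the loss is 60 − 48 = 12 points. Of these, 58 − 48 = 10 come from Fisher's discreteness and 60 − 58 = 2 from omitting the stratum. At 84:52 the loss is 85 − 81 = 4 points. With a continuity correction, CMH at 36:36 and 30%/50% has power of only 50%, so the correction removes most of the gain.

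**Step 3. Pooled cohorts with different rates and no drug effect.** Take 48:16 plus 30:30, with 60% response in part 1 and 40% in part 2.

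- Active: (48 × 0.6 + 30 × 0.4)/78 = 40.8/78 = 52.3%.
- Placebo: (16 × 0.6 + 30 × 0.4)/46 = 21.6/46 = 47.0%.

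The collapsed table therefore shows a 5.3-point difference that allocation alone creates. Simulated size:

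| Rates, part 1 / part 2 | Fisher | CMH, CSBM stratum | CMH, CSBM stratum × cohort |
|---|---|---|---|
| 50% / 50% | 4.0% | 4.9% | 4.9% |
| 50% / 40% | 4.7% | 5.7% | 4.9% |
| 60% / 40% | 7.0% | 8.2% | 4.9% |

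**Step 4. Price of adding cohort.** At 48:16 plus 30:30 with equal cohort rates and odds ratio 3, power for Fisher and for CMH on stratum × cohort is 79.8% and 79.3% (placebo rates 30%/30%), 75.4% and 76.9% (20%/40%), and 55.9% and 67.6% (10%/50%). When the strata are similar, the pooled gain is therefore control of size, not power.

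**The case against.** A specific endpoint section may qualify a general rule. Fisher's test agrees with the protocol, and CMH on the right strata is at least foreseen. The endpoints are secondary in a phase 2b trial, and while cohort response rates are equal the error is conservative. All of this stands, and it limits the weight of the point. It does not settle which test counts or when CMH applies.

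Three stronger readings are tempting and are not supported.

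- *That response must depend strongly on stratum because the definition includes an absolute rate of 3 per week.* Response is a rise of at least 1 or a rate of at least 3. For a baseline of 2.0 or less, reaching 3 already means a rise of at least 1, so the absolute limb matters only above 2.0, in part of the upper stratum. SBM response is linked less directly still, because the strata are defined on CSBM rate.
- *That the trial loses 20 or more points of power because it ignores the strata.* That needs contrasts such as 20%/75%, which have no source in the documents, and part 2 taken alone. At modest contrasts nearly all of the loss is discreteness.
- *That the unadjusted odds ratio is wrong.* A common odds ratio of 3 becomes 2.86 in the collapsed table at 30%/50%. That is a marginal odds ratio, a different quantity, because odds ratios do not collapse over strata.

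It is also fair to say that the plan does not state outright that the responder analysis pools the cohorts. Listing cohort under Subpopulations, and sizing part 2 by conditional power, suggest that it does.

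**Conclusion.** The inconsistency is in the text and does not depend on any assumed rate: SAP 4.6.4 and Protocol 9.2.4.2 leave unadjusted what SAP 4.2 says will be adjusted, and the CMH option has no trigger and no stated standing.

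The size of the effect does depend on assumptions. With equal cohort response rates, Fisher's true size is roughly 1-4%. Against uncorrected CMH on CSBM stratum at odds ratio 3, the loss is about 10-12 points at 36:36 and about 4 at 84:52 when the strata differ modestly, and more if they differ further. A reader might infer that the tests are always conservative. They are not if the cohorts are pooled with different response rates: at 60% and 40%, Fisher reaches about 7% and CMH on CSBM stratum alone about 8%.

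A reader might also infer that the trial's conclusion is at risk. It is not: SAP 4.6.3 defines success by the primary ANCOVA alone, and the tests discussed here are secondary or exploratory. The change should be made, but the point is moderate.

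**What to change.** In SAP 4.6.4 and Protocol 9.2.4.2:

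- State whether the responder analysis is pooled over cohorts or by cohort.
- Make CMH without continuity correction the test of record, stratified by CSBM randomization stratum, and by cohort as well when the cohorts are pooled. Report the Mantel-Haenszel common odds ratio with its 95% CI.
- Replace the open condition on sufficient numbers with a numeric trigger for an exact stratified test. Set the trigger on totals over the strata. A rule of expected count 5 within each stratum would almost always fire in part 1: with equal strata the placebo group is 16/2 = 8, and 8 × 0.3 = 2.4.
- Keep unstratified Fisher as a sensitivity analysis.

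For SAPS-PD response (SAP 4.6.5), which covers a smaller subset, use the exact stratified test directly. Record the change in SAP section 5, which at present reports none from the protocol.

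The cost is wording; no new data are needed. Stratifying by cohort gives up a little power when cohort rates are equal (79.3% against 82.0% for CMH on CSBM stratum alone, at placebo rates of 30%/30% and odds ratio 3). Because an unblinded interim analysis of part 1 has been done, the amendment should be dated and justified on design grounds alone.

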4 STUDY DESCRIPTION

The first part of this Phase 2b study was conducted as a multicenter, randomized, double-blind, placebo-controlled study. Each subject's total study duration was no more than 10 weeks and total active dosing days were 25 days. 72 subjects were randomized in a 3:1 ratio to active treatment or placebo, respectively. 54 subjects received active treatment and 18 received placebo. Randomization was stratified on baseline weekly CSBM rate. Subjects with baseline CSBM rates of 1.0-3.0/week were randomized to begin with 75 mg of ENT-01 (3 tablets) or 3 placebo tablets: subjects with baseline CSBM rates of 0-0.9/week were randomized to begin with 150 mg of ENT-01 (6 tablets) or 6 placebo tablets. The dose was then escalated every 3 days in increments of 25 mg (or 1 placebo tablet) until either an effective dose, a maximum tolerated dose or 250 mg was reached, whichever came first. The dose was then "fixed" at that dose for the remainder of the 25-day treatment period.

In this amendment of the protocol, the study will be conducted as a multicenter, randomized double-blind, placebo-controlled study. Each subject's total study duration will be no more than 10 weeks and total active dosing days will be 25 days. Up to 80 subjects will be randomized across up to 25 U.S. sites to ensure approximately 60 subjects will complete all visits, assuming a 25% early termination rate. Randomization will be 1:1 to active treatment or placebo.

Randomization will be stratified based on baseline weekly CSBM rate. Subjects with baseline CSBM rates of 1.0-3.0/week will be randomized to begin with 75 mg of ENT-01 (3 tablets) or 3 placebo tablets: subjects with baseline CSBM rates of 0-0.9/week will be randomized to begin with 150 mg of ENT-01 (6 tablets) or 6 placebo tablets. The dose will then be escalated every 3 days in increments of 25 mg (or 1 placebo tablet) until either an effective dose, a maximum tolerated dose or 250 mg is reached, whichever comes first. The dose will then be “fixed” at that dose for the remainder of the 25-day treatment period. The dosing logic is illustrated in the diagram below.

- The subject will be randomized to either placebo or ENT-01, with the starting number of tablets based on the baseline CSBM rate.
- The dose will be escalated every 3 days by 1 tablet (25mg ENT-01 or placebo)
- If the subject passes at least 1 CSBM/day on each of 3 consecutive days the dose is “fixed.” Otherwise, the dose is escalated.

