4.2 Visit 2: Randomization (Study Day 1 + 8 days)

The purpose of this period is to establish the prokinetic dose for subjects randomized to treatment (or placebo). The prokinetic dose is the dose that results in a CSBM on all three dosing days at any given dose. Subjects will also be required to have a CSBM on at least 1 of 2 subsequent days at the “fixed” dose. In other words, *the dose will only be “fixed” for the remainder of the treatment period if the subject has CSBMs on at least 4 of 5 consecutive days at a given dose.*

In this amended study, subjects will be randomized in a 1:1 ratio to receive either ENT-01 or placebo depending on baseline weekly CSBM rate:

- Subjects with baseline CSBMs of 0-0.9 will be randomized to begin treatment with 150 mg of ENT-01 or 6 tablets of placebo.
- Subjects with baseline CSBMs of 1.0-3.0 will be randomized to begin with 75 mg of ENT-01 or 3 tablets of placebo.

Subjects will self-administer the study medication at home, beginning the day after Visit 2. The dose will be taken upon awakening on an empty stomach along with 8 oz. of water. The subject will be instructed to remain in the upright position for the next 60 minutes. This can be in the sitting or standing position, and the subject should be encouraged to walk around, go to the kitchen and make a cup of tea or coffee (with or without milk or sugar), to watch the news or read a paper in the upright position. The subject will also be instructed to not eat for at least 60 minutes thereafter.

After the first dose, the subject will be advised to stay home for 4-6 hours in case an emergency evacuation occurs. The subject can determine what to do after subsequent doses. Subjects are not allowed to miss a dose, however, in the event this does happen, subjects must wait a minimum of 5 hours post ingestion of a meal and at least 1 hour prior to the next meal to take the missed dose.

Any given dose is repeated for 3 consecutive days. If the subject has not produced a CSBM

within 24 hours of a dose on all three days at the initial dose, then they will increase their daily dose by 1 tablet (i.e., 25 mg for active treatment), repeating that dose for three consecutive days. This 3-day incremental dosing will continue until the subject:

- Reaches the prokinetic dose. The prokinetic dose is determined when a subject has entered CSBMs on at least 4 of 5 consecutive days at a given dose. The subject then remains on that dose until Visit 4;

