1.2.2 Secondary Objectives

The secondary objectives include:

- To determine if the correct starting dose (75mg or 150mg) can be predicted from the baseline weekly CSBM rate.
- To collect information on the effect of ENT-01 on CSBM, SBM, ease of passage, consistency, suppository/enema use and subjective bowel function and quality of life (QOL).

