2.6.2 Secondary Efficacy Endpoints

The secondary efficacy endpoints include:

- Frequency of dose adjustments in the Dose Adjustment period: The number of dose adjustments a subject has from the initial starting dose to the subject's fixed dose.
- Prokinetic bowel response during the Fixed Dose period: A prokinetic response is defined as a weekly CSBM rate increase of 1 or more compared to baseline or an absolute rate of 3 or more CSBMs per week.
- Change from baseline in the weekly SBM rate during the Fixed Dose period: An SBM is a bowel movement which did not occur within 24 hours after taking rescue medication.
- SBM bowel response to ENT-01 during the Fixed Dose period: An SBM bowel response is defined as a weekly SBM rate increase of 1 or more compared to baseline or an absolute rate of 3 or more SBMs per week.
- Change from baseline in stool ease of passage during the Fixed Dose period: Stool ease of passage is rated on a 1-7 ordinal point scale (see [APPENDIX 4](#) of the Protocol). A subject's ease of passage score for a given time period is the average of the ease of passage scores associated with SBMs during that time period.
- Change from baseline in stool consistency during the Fixed Dose period: Stool consistency is measured using the 7-point Bristol Stool Chart (see [APPENDIX 5](#) of the Protocol). A subject's stool consistency score for a given time period is the average of the stool consistency scores associated with SBMs during that time period.
- Change from baseline in suppository/enema use during the Fixed Dose period: Suppository/enema use is measured as a weekly average during the Fixed Dose period. This is captured in the subject stool diary.
- Time to first CSBM in the Fixed Dose period: Time to first CSBM in the Fixed Dose period is defined as the time from the subject taking the first dose of study medication in the Fixed Dose period until the subject has a CSBM.
- Time to first SBM in the Fixed Dose period: Time to first SBM in the Fixed Dose period is defined as the time from the subject taking the first dose of study medication in the Fixed Dose period until the subject has an SBM.
- Time to first rescue medication use in the Fixed Dose period: Time to first rescue medication use in the Fixed Dose period is defined as the time from the subject taking the first dose of study medication in the Fixed Dose period until the subject first uses rescue medication.

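### A difference between baseline strata in the number of dose adjustments is not evidence that baseline CSBM rate predicts the starting dose, because each stratum climbs from a different dose

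*SAP*

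**What the plan says.** SAP 1.2.2 lists the objective first among the secondary objectives: "To determine if the correct starting dose (75mg or 150mg) can be predicted from the baseline weekly CSBM rate". Protocol 3.2 does the same. The endpoint that bears on it, in SAP 2.6.2 and Protocol 3.2, is "The number of dose adjustments a subject has from the initial starting dose to the subject's fixed dose".

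The analysis in SAP 4.6.4 is one sentence: "The frequency of dose adjustment will be summarized by treatment groups and baseline CSBM strata and no formal test will be performed". The rest of that sentence limits the absence of a test to the comparison of treatment groups. Protocol 9.2.4.2 plans the same summary. Neither document specifies a contrast between strata, a definition of a correct starting dose, or a prediction analysis.

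The dosing rules are in Protocol 4 and 4.2. For the low stratum: "Subjects with baseline CSBMs of 0-0.9 will be randomized to begin treatment with 150 mg of ENT-01 or 6 tablets of placebo". For the high stratum: "Subjects with baseline CSBMs of 1.0-3.0 will be randomized to begin with 75 mg of ENT-01 or 3 tablets of placebo". Both then rise by one 25 mg tablet every three days "until either an effective dose, a maximum tolerated dose or 250 mg is reached, whichever comes first". Protocol 4.2 also allows one 25 mg reduction for diarrhea, after which the dose is fixed. A subject without a response at 250 mg stays on that dose to the end of treatment.

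**The concern.** Starting dose and baseline stratum are the same variable in this design. Nobody at a given baseline is randomized between 75 and 150 mg. A count measured from the starting dose therefore has a different zero and a different ceiling in each stratum. Two subjects who both need 200 mg score 2 steps in the low-baseline stratum and 5 in the high-baseline stratum. Zero steps in the low stratum covers every need up to and including 150 mg.

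The count also does not say why a subject stopped climbing. Fixing because of response, fixing at the highest dose without a dose-limiting event, and arriving at 250 mg without a response can all give the same number.

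At stake is the reading of a stated secondary objective. Fewer adjustments at low baseline could be reported as a sign that the baseline rule picks the starting dose well, when the ladder alone can produce that pattern.

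**Working it through.** **Inputs from the documents.** Starting doses 150 mg (baseline 0-0.9) and 75 mg (baseline 1.0-3.0); step 25 mg every 3 days; maximum 250 mg; at most 25 treatment days (Protocol 4 and 4.2). The required dose D and the daily response chance q used below are assumptions, shown over a range.

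**1. Check of the ladder.** The plan gives no figure for this endpoint, but SAP 4.8.10 has a worked example: a low-baseline patient whose highest dose is 200 mg is included at 150, 175 and 200 mg. That is (200 − 150)/25 = 2 steps, as the ladder predicts.

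**2. Maximum escalations.** (250 − 150)/25 = 4 and (250 − 75)/25 = 7. Both fit in 25 days: 250 mg is first taken on day 1 + 3×4 = 13 or day 1 + 3×7 = 22. Each failed first fix adds 2 days, so from 75 mg one failure still fits (day 24) and two do not (day 26). The diarrhea reduction could bring the literal number of adjustments to 5 or 8; the documents do not say whether a reduction counts.

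**3. Same need in both strata, so baseline predicts nothing.** Steps = max(0, (D − start)/25).

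| Required dose | 150 mg start | 75 mg start | Gap |
|---|---|---|---|
| all 75 mg | 0 | 0 | 0 |
| all 100 mg | 0 | 1 | 1 |
| all 150 mg | 0 | 3 | 3 |
| all 200 mg | 2 | 5 | 3 |
| all 250 mg | 4 | 7 | 3 |
| uniform on 75, 100, …, 250 mg | 1.25 | 3.50 | 2.25 |

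The uniform row is (0+0+0+0+1+2+3+4)/8 = 1.25 and (0+1+…+7)/8 = 3.50. The share with no adjustment is 4/8 = 50% against 1/8 = 12.5%. For any D up to 150 mg the gap is (D − 75)/25; from 150 mg upward it is 3.

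**4. Low-baseline subjects truly need more.** Shift the uniform need in the low stratum up by 75 mg, capped at 250 mg. Needs become 150, 175, 200, 225 and four at 250, with mean 1750/8 = 218.75 mg against 162.5 mg. Mean steps are (0+1+2+3+4+4+4+4)/8 = 2.75 against 3.50. The stratum with the higher need still shows fewer steps.

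**5. Dose has no effect.** Give both strata the same daily chance q of a CSBM at every dose and apply the Protocol's rule (three days, then one of two) and the 25-day limit; 40,000 simulated subjects per cell.

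| q | 150 mg start | 75 mg start |
|---|---|---|
| 0.1 | 4.00 | 6.99 |
| 0.3 | 3.86 | 6.63 |
| 0.5 | 3.14 | 4.80 |
| 0.8 | 0.96 | 1.02 |
| 0.9 | 0.39 | 0.39 |

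The ceiling alone separates the counts when response is infrequent; they converge when it is frequent.

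**6. A quantity on a common scale.** Needing more than 150 mg means at least 1 step from 150 mg or at least 4 steps from 75 mg. Under the uniform null of step 3 this is 4/8 = 50% in both strata. Mean fixed dose does not have this property: (4×150 + 175 + 200 + 225 + 250)/8 = 181.25 mg against 162.5 mg under the same null, because needs below 150 mg are not seen in the low stratum.

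The share above 150 mg is equal only if need is driven by dose. If dose has no effect and q = 0.8, the chance of fixing at any one dose is 0.8³ × (1 − 0.2²) = 0.512 × 0.96 = 0.49. The share is then 0.51 in the low stratum and 0.51⁴ ≈ 0.07 in the high one. Placebo subjects, who climb the same tablet ladder, show how large this effect is.

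**The case against.** The plan makes no claim about strata. It contains no between-stratum contrast, and within one stratum the count is the distance from the assigned start, which does bear on whether that start was enough. Because each stratum has one known start, fixed dose is recoverable as start + 25 mg × net steps, and the share above 150 mg can be read from the same table. Placebo columns are planned. Endpoints are also summarized by stratum (SAP 4.2) and by fixed dose (SAP 4.6.4), and dose-limiting events by dose level (SAP 4.8.10). Neither document maps endpoints to objectives, so calling this the only endpoint for the objective is an inference.

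Most of this stands. A reader might infer that the objective cannot be answered at all from these data, or that low-baseline subjects will look well matched whatever the truth. The documents do not support either. If all low-baseline subjects needed 250 mg and all high-baseline subjects 75 to 100 mg, the table would show 4 steps against 0 to 1. A reader might also take the absence of a formal test as a decision about the strata; that sentence concerns ENT-01 against placebo.

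What the objection does not remove: no planned output crosses dose in mg with stratum and reason for stopping, and nothing tells the reader that the two counts are on different scales.

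**Conclusion.** The point holds in this form: a difference between strata in raw adjustment counts is not evidence on whether baseline predicts the starting dose. If the required dose is distributed alike in both strata, the 75 mg starters show 0 to 3 more steps on average, 2.25 more under an assumed uniform need. The gap is zero if everyone fixes at the starting dose, and negligible if response is frequent whatever the dose. The maxima of 4 and 7 follow from the documents; the size of the gap depends on the assumed need or response rate.

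The planned table is biased between strata and silent on the reason for stopping, but it is not empty, and the underlying data allow a better summary. One limit is built into the design: no subject with baseline 0-0.9 starts below 150 mg, so the trial cannot show whether less would have been enough for them. The success criterion in SAP 4.6.3 is not touched.

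**What to change.** Keep the count as a descriptive summary and say whether a reduction is counted. For the starting-dose objective, add to SAP 4.6.4:

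- A table by stratum, for ENT-01 with placebo alongside as a benchmark for ladder and time effects, of the dose in mg at which the prokinetic criterion was first met, split by reason for fixing: response, intolerance, or 250 mg without response.
- The share needing more than 150 mg in each stratum (at least 1 step against at least 4), read next to the placebo share.
- A statement that the trial cannot show whether a dose below 150 mg would suffice at baseline 0-0.9, and that raw counts are not to be compared between strata.

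A censored-data model of dose against baseline is an optional supplement. It would rest on distributional assumptions below 150 mg in the low stratum, and it needs a sensitivity analysis because censoring at intolerance may be informative.

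First, the passages on the fixing criterion must be reconciled. SAP 2.1 describes two CSBMs in three days; Protocol 4 and 4.2 describe CSBMs on three consecutive days and then on at least one of the next two. The table depends on which rule is meant.

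Cost: one extra table and some SAP wording, with no new data.
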